7.2.3 NCI-IRB Reporting of IND Safety Reports

Only IND Safety Reports that meet the definition of an unanticipated problem will need to be reported to the NCI IRB.

7.3 IND SPONSOR REPORTING CRITERIA

An investigator must **immediately** report to the sponsor using the mandatory MedWatch form 3500a any serious adverse event, whether or not considered drug related, including those listed in the protocol or investigator brochure and must include an assessment of whether there is a reasonable possibility that the drug caused the event.

- All Grade 5 (fatal) events (except death due to progressive disease) must be reported via email within 24 hours. A complete report must be submitted within one business day.
- All other serious adverse events including deaths due to progressive disease must be reported within one business day

Study endpoints that are serious adverse events (e.g. all-cause mortality) must be reported in accordance with the protocol unless there is evidence suggesting a causal relationship between the drug and the event (e.g. death from anaphylaxis). In that case, the investigator must immediately report the death to the sponsor.

Events will be submitted to the Center for Cancer Research (CCR) at: [contact] and to the CCR PI and study coordinator.

7.3.1 Reporting Pregnancy

7.3.1.1 Maternal exposure

If a patient becomes pregnant during the course of the study, the study treatment should be discontinued immediately and the pregnancy reported to the Sponsor. The potential risk of exposure of the fetus to the Tremelimumab should be documented in box B5 of the MedWatch form "Describe Event or Problem".

Pregnancy itself is not regarded as an SAE. However, as patients who become pregnant on study risk intrauterine exposure of the fetus to Tremelimumab which may be teratogenic, the CCR is requesting that pregnancy should be reported in an expedited manner as Grade 3 "Pregnancy, puerperium and perinatal conditions - Other (pregnancy)" under the Pregnancy, puerperium and perinatal conditions SOC.

Congenital abnormalities or birth defects and spontaneous miscarriages should be reported and handled as SAEs. Elective abortions without complications should not be handled as AEs. The outcome of all pregnancies (spontaneous miscarriage, elective termination, ectopic pregnancy, normal birth, or congenital abnormality) should be followed up and documented.

If any pregnancy occurs in the course of the study, then the investigator should inform the Sponsor within 1 day, i.e., immediately, but no later than 24 hours of when he or she becomes aware of it.

The designated Sponsor representative will work with the investigator to ensure that all relevant information is provided to the Sponsor within 1 to 5 calendar days for SAEs and within 30 days for all other pregnancies.

The same timelines apply when outcome information is available.

7.3.1.2 Paternal exposure

Male patients should refrain from fathering a child or donating sperm during the study and for 3 months after the last dose of Tremelimumab.

Pregnancy of the patient's partner is not considered to be an AE. However, the outcome of all pregnancies (spontaneous miscarriage, elective termination, ectopic pregnancy, normal birth, or congenital abnormality) occurring from the date of the first dose until 3 months after the last dose of Tremelimumab should, if possible, be followed up and documented.

7.5 DATA AND SAFETY MONITORING PLAN

7.5.1 Principal Investigator/Research Team

The clinical research team will meet on a regular basis when patients are being actively treated on the trial to discuss each patient. Decisions about dose level enrollment and dose escalation if applicable will be made based on the toxicity data from prior patients.

All data will be collected in a timely manner and reviewed by the principal investigator or a lead associate investigator. Adverse events will be reported as required above. Any safety concerns, new information that might affect either the ethical and or scientific conduct of the trial, or protocol deviations will be immediately reported to the IRB using iRIS and to the Sponsor.

The principal investigator will review adverse event and response data on each patient to ensure safety and data accuracy. The principal investigator will personally conduct or supervise the investigation and provide appropriate delegation of responsibilities to other members of the research staff.

7.5.2 Sponsor Monitoring Plan

As a sponsor for clinical trials, FDA regulations require the CCR to maintain a monitoring program. The CCR's program allows for confirmation of: study data, specifically data that could affect the interpretation of primary study endpoints; adherence to the protocol, regulations, and SOPs; and human subjects protection. This is done through independent verification of study data with source documentation focusing on:

- Informed consent process

- Eligibility confirmation
- Drug administration and accountability
- Adverse events monitoring
- Response assessment.

The monitoring program also extends to multi-site research when the CCR is the coordinating center.

This trial will be monitored by personnel employed by an NCI contractor. Monitors are qualified by training and experience to monitor the progress of clinical trials. Personnel monitoring this study will not be affiliated in any way with the trial conduct.

8 STATISTICAL CONSIDERATIONS

The primary objective of this pilot study is to determine if it is feasible to administer three doses of Tremelimumab to patients with hepatocellular carcinoma (HCC) and to determine clinical efficacy in several cohorts of patients. Secondary objectives include examining a variety of immunologic parameters prior to treatment and after treatment to determine if there is evidence of patients exhibiting an immune response to treatment, to assess safety and toxicity and to determine the feasibility of administering 3 doses of tremelimumab in addition to RFA in patients with biliary tract cancer.

8.1 COHORTS A AND B

Relative to the feasibility endpoint, this will be decided in Cohorts A and B; all patients enrolled into Cohorts A and B at the 10 mg/kg dose level will be considered as one group for feasibility evaluation. Feasibility will be evaluated in the first 20 evaluable patients enrolled in in these two cohorts on this trial at the 10mg/kg dose level following a dose-escalation phase of 3-6 patients treated at 3.5mg/kg dose level. The safety of the 10 mg/kg dose level will be evaluated in the first 3-6 patients treated at that dose. If there are 2 or more DLTs among the first 3-6 patients treated at this level, then accrual would stop. Regarding feasibility, it would be desirable if the fraction of patients who could receive three doses of the monoclonal antibody were consistent with 80% or higher and greater than 50%. With 20 evaluable patients, if there are 14 or more patients who are able to receive three doses of the monoclonal antibody, then there is a 5.8% probability of this being true if the true probability of an individual patient being able to receive this much antibody were 50% and there is a 91.3% probability of this being true if the true probability for an individual were 80%. Thus, 14 or more out of 20 patients receiving three doses of antibody would provide strong evidence that it is feasible to administer this antibody in a substantial fraction of patients, consistent with 80% or more and this would be considered a successful outcome for the trial.

Prior to amendment G, administration of three doses has been determined to be feasible based on the first 20 total patients enrolled and the feasibility evaluation was considered to have ended at that point. Evaluations for clinical efficacy will be the primary objective from this point forward.

With amendment G, there will be 20 patients enrolled in cohort A at 10mg/kg (10 receiving RFA and 10 receiving TACE).

Each of these sub-cohorts will be evaluated for efficacy as follows. In each sub-cohort of 10 patients the trial will have 82% power to rule out 15% 6 month as the proportion stable at 6

months in favor of 50% being stable at 6 months, with each evaluation assuming that a one-sided 0.10 significance level exact binomial test would be performed. If there are 3 patients in 10 who are able to have stable disease at a 6 month evaluation, then the lower one-sided 90% confidence bound for 3/10 is 11.6% (the two sided 80% confidence interval extends from 11.6% to 55.2%). Similarly, with 4 in 10 with stable disease at 6 months, the lower one-sided 90% confidence bound for 4/10 is 18.8% (the two sided 80% confidence interval extends from 18.8% to 64.6%). Thus, in Cohort A, 3 or 4 patients out of 10 attaining stable disease at 6 months with either TACE or RFA would rule out 10-15% as the fraction who would do so, with 90% one sided confidence. The results from the two sub-cohorts of cohort A treated at 10 mg/kg may also have their results combined in an exploratory fashion to report their overall efficacy.

Also by Amendment G, cohort B will be expanded to allow 20 evaluable patients to be enrolled for efficacy. With this number of patients, this cohort will have 97% power to rule out 15% as the proportion stable at 6 months in favor of 50% being stable at 6 months, with the evaluation assuming that a one-sided 0.10 significance level exact binomial test would be performed. If there are 6 patients in 20 who are able to have stable disease at a 6 month evaluation, then the lower one-sided 90% confidence bound for 6/20 is 16.6% (the two sided 80% confidence interval extends from 16.6% to 46.7%). Thus, in cohort B, having 6 or greater patients attaining stable disease at 6 months would rule out 15% as the fraction who would do so, with 90% one-sided confidence.

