1 INTRODUCTION

1.1 STUDY OBJECTIVES

1.1.1 Primary:

To assess the safety and feasibility of combining Tremelimumab with trans-arterial catheter chemoembolization (TACE) or radiofrequency ablation (RFA) in patients with advanced HCC.

1.1.2 Secondary:

To evaluate clinical indicators of efficacy (response rate, time to tumor progression, overall survival) in patients with advanced HCC undergoing TACE or radiofrequency ablation (RFA) in combination with Tremelimumab.

1.1.3 Exploratory:

1.1.3.1 To evaluate changes in immune parameters as well as pharmacokinetics in the peripheral blood of patients with advanced HCC undergoing TACE or radiofrequency ablation (RFA) in combination with Tremelimumab

1.1.3.2 Following amendment F we will evaluate safety and feasibility of combining Tremelimumab with cryoablation in patients with advanced HCC and radiofrequency ablation (RFA) in advanced intrahepatic cholangiocarcinoma.

1.1.3.3 To evaluate changes in immune parameters as well as pharmacokinetics in the peripheral blood of patients with advanced HCC or intrahepatic cholangiocarcinoma undergoing TACE, radiofrequency ablation (RFA) or cryoablation in combination with Tremelimumab.

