3.2 SCHEDULE

- Day 1: Tremelimumab IV every 4 weeks x 6 doses and then every 12 weeks for 2 years or until disease progression whichever comes first.
- Day 36 [+/- 96 hours]: RFA or TACE.
- Restaging CT /MRI scan every 8 weeks to evaluate TTP in target lesion. (Both standard RECIST and Immune-related Response Criteria [irRC] will be employed).
- Dose: (Cohort A only): Initially three to six patients will be treated at 3.5mg/kg (with subsequent dosing also at 3.5mg/kg) prior to enrolling to the 10mg/kg dose level. If a single patient experiences dose-limiting toxicity (DLT) related to the combination this cohort will be expanded to N=6 as per a standard 3+3 design. If 3.5mg/kg is established to be safe we will proceed to the 10mg/kg dose level. N=20 patients in cohort A will be treated at 10mg/kg.
- For Cohort A (BCLC Stage C patients): TACE or radiofrequency ablation (RFA) will be performed once only.
- For Cohort B (BCLC Stage B patients): TACE may be repeated (as per standard of care) on months 3, 7, and 13, and q6 months thereafter (if indicated).
- Cohort B will only be recruited following completion of the dose-escalation portion of Cohort A.

For Cohort E (BTC patients, status post prior chemotherapy with intrahepatic disease) RFA will be performed once only, also on Day 36 (+/- 96hrs).

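### The feasibility rule counts three antibody doses only, so it does not measure the primary objective, which is feasibility of tremelimumab combined with TACE or RFA

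*Combined protocol and SAP*

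**What the plan says.** Section 1.1.1 gives the primary objective: "To assess the safety and feasibility of combining Tremelimumab with trans-arterial catheter chemoembolization (TACE) or radiofrequency ablation (RFA) in patients with advanced HCC". Section 8 restates it for HCC as the feasibility of giving three doses of the antibody and leaves the procedure out. For biliary tract patients the same paragraph does name the procedure, as a secondary objective: "to determine the feasibility of administering 3 doses of tremelimumab in addition to RFA in patients with biliary tract cancer".

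Section 8.1 sets the rule for Cohorts A and B at 10 mg/kg: "Feasibility will be evaluated in the first 20 evaluable patients enrolled in in these two cohorts", with success "if there are 14 or more patients who are able to receive three doses of the monoclonal antibody". It gives a pass probability of 5.8% at a true rate of 50% and 91.3% at 80%. It adds that, before amendment G, three-dose administration had been found feasible and the evaluation had ended.

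Two other places use the result more broadly. Section 3.1 ties the additional cohorts to Cohort A having shown feasibility of ablation together with tremelimumab. Section 8.2 cites 9 of 10 patients meeting the feasibility goal as the reason for giving Cohorts D and E a clinical-benefit goal. The only numerical feasibility goal in the plan is the antibody count.

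Section 3.2 schedules the procedure: "Day 36 [+/- 96 hours]: RFA or TACE".

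**The concern.** The objective has two components and the success rule checks one. A patient whose procedure was cancelled or proved impossible, but who received dose 3, meets the rule. If that happened in more than a few patients, the trial could conclude that the combination is feasible when it was not delivered often enough to support that. What is at stake is how the Cohort A and B result may be worded, and whether the joint feasibility objectives for Cohorts D and E get a matching summary. The sample size, the threshold and the stated probabilities are not in question.

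**Working it through.** **1. Timing.** Doses every 4 weeks from Day 1 fall on Day 1, Day 1 + 28 = 29 and Day 29 + 28 = 57 (section 3.2). The procedure is due on Day 36, with a window of 96 h = 4 days either side, so Days 32 to 40. A patient treated to plan therefore has the procedure between doses 2 and 3.

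**2. Does anything make dose 3, or being counted, depend on the procedure?** The removal criteria in section 3.12.1 do not list a missed procedure. Section 6.3.1 defines evaluability for toxicity (from the first antibody dose) and for response (measurable disease, one cycle, re-evaluation). Neither requires the procedure, and there is no definition for feasibility. I found no such condition in the text available to me, where the study calendar (section 3.11) appears only in part.

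**3. The plan's own figures.** With X the number of successes in 20,

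P(X ≥ 14 | p) = Σ (x = 14 to 20) C(20, x) pˣ (1 − p)²⁰⁻ˣ

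- p = 0.50: 0.0577, which is the stated 5.8%.
- p = 0.80: 0.9133, which is the stated 91.3%.

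Both reproduce.

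**4. A joint rule.** Let q be the share of three-dose patients who also had the procedure. The documents do not give q, so the values below are assumptions. With an antibody rate of 0.80 (the plan's target), the joint rate is 0.80 × q. Because q is conditional on three doses, no independence assumption is needed.

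| q (assumed) | Joint rate | P(joint count ≥ 14) | P(antibody count ≥ 14) |
|---|---|---|---|
| 100% | 80% | 91.3% | 91.3% |
| 95% | 76% | 81.6% | 91.3% |
| 90% | 72% | 68.3% | 91.3% |
| 80% | 64% | 38.0% | 91.3% |

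**5. The same question at the unacceptable rate.** Hold the joint rate at 50%. The antibody rate is then 0.50 / q, and the antibody-only rule passes with:

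- q = 95%: antibody rate 52.6%, probability 9.0%
- q = 90%: antibody rate 55.6%, probability 14.1%
- q = 80%: antibody rate 62.5%, probability 32.8%

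The nominal figure is 5.8%.

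**6. How many missed procedures would matter.** The joint count falls below 14 once the number of three-dose patients without a procedure reaches the antibody count minus 13. At an antibody count of 14, one is enough: 13 of 20 has probability 13.2% or more under p = 0.50, against 5.8% for 14. At 18, it takes five. The final antibody count is not stated.

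**7. Threshold.** If the joint endpoint itself is judged against 50% and 80%, at least 14 of 20 keeps 5.8% and 91.3%. Neither n nor the cut-off needs to change.

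**The case against.** The case for leaving the plan alone has substance.

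- **Section 8.1 words its own inference as feasibility of the antibody.** That is true of that section. It does not settle the matter, because section 1.1.1 states the objective for the combination and sections 3.1 and 8.2 rely on the result in that sense.
- **Three doses is a sensible marker.** For a patient treated to plan, dose 3 comes after the procedure. Entry requires technically amenable disease and tumor board review with interventional radiology (section 2.1.1.3), and section 3.1 lets Cohort A have either RFA or TACE. This makes a high q plausible. It does not show that the procedure was delivered five weeks later.
- **The evaluable set might already require the procedure.** This cannot be excluded, since the term is undefined for feasibility and the closing statement in section 8.1 speaks of total patients enrolled. If such patients were replaced, non-delivery would leave the denominator and be hidden in another way.
- **The Cohort A and B evaluation is closed.** This stands. Redefining success now would change an endpoint after its result is known, so the remedy is added reporting.

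A reader might also infer more than the documents support:

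- That the combination may have reached only half the patients while the rule passed with 91.3% probability. This needs q = 62.5%, a value obtained by solving 0.80 × q = 0.50. Nothing in the documents suggests it.
- That a procedure outside the Day 36 window is a feasibility failure. A late procedure has still been delivered; timing is a separate matter.
- That the 14-of-20 rule fails Cohort E. Section 8.1 applies it to Cohorts A and B only. Cohort E's objective is already worded jointly, is secondary, and has no antibody-only rule to correct.

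**Conclusion.** The mismatch is real: the primary objective concerns the combination, the rule counts the antibody, and the plan uses the result as if it covered both. Its size is unknown because q is not reported. Under the plan's 80% antibody rate, the chance of passing on joint delivery is 91.3% if every three-dose patient had the procedure, and 81.6%, 68.3% and 38.0% at 95%, 90% and 80%. If q was 100%, nothing changes.

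The documents do not show that the combination was infeasible or that the antibody conclusion is wrong. They show that the existing rule alone cannot support a conclusion about the combination. This rests on the text available, with evaluable undefined for feasibility and the study calendar incomplete.

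**What to change.** For the same first 20 patients, report beside the existing result:

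1. the number who received three doses;
2. the number who had TACE or RFA, with timing relative to Day 36 ± 96 h shown separately and not as a condition of success;
3. the number with both.

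Do not exclude patients for lacking the procedure. State which 20 patients these are and what evaluable meant. Limit the feasibility conclusion to the antibody unless the joint count also reaches 14. Label the joint count as added after the Cohort A and B evaluation closed.

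Report the same joint count descriptively for Cohort E (three doses plus RFA, as section 8 words it) and for Cohort D (three doses plus cryoablation, under section 1.1.3.2). Sample size and threshold stay as they are.

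The cost is one extra table and possibly a lower reported feasibility rate. Section 4 already requires interventions during the study to be recorded on the case report form, so the data should exist.

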2 ELIGIBILITY ASSESSMENT AND ENROLLMENT

2.1 ELIGIBILITY CRITERIA

2.1.1 Inclusion Criteria

2.1.1.1 Patients must have histopathological confirmation of hepatocellular carcinoma (HCC) or (Cohort E only) biliary tract carcinoma (BTC) by the Laboratory of Pathology of the NCI prior to entering this study OR histopathological confirmation of carcinoma in the setting of clinical and radiological characteristics which, together with the pathology, are highly suggestive of a diagnosis of HCC (or biliary tract carcinoma in Cohort E). Fibrolammellar variant is also allowed. For cohort E, the term BTC includes intra- or extrahepatic cholangiocarcinoma, gallbladder cancer or ampullary cancer, as long as there is an intrahepatic component amenable to RFA.

2.1.1.2 Patients must have disease that is not amenable to potentially curative resection, transplantation or ablation. For Cohorts A and D patients must have progressed on, been intolerant to, or refused prior sorafenib therapy. Cohort E patients must have received at least one line of chemotherapy for BTC.

2.1.1.3 Disease must be technically amenable to transhepatic arterial chemoembolization (TACE), radiofrequency ablation (RFA), or cryoablation. Each case will be discussed at GI tumor board with interventional radiology. Patients must have evaluable disease.

2.1.1.4 If liver cirrhosis is present, patient must have a Child-Pugh A/B7 classification (see Appendix B section 12.2).

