3 STUDY IMPLEMENTATION

3.1 STUDY DESIGN

- The proposed study is a pilot study of Tremelimumab - at a planned dose 10mg/kg/IV q 4 weekly - in patients with advanced HCC treated with either TACE or RFA.

The initial study population is Cohort A as described below and these patients will be treated with either RFA or TACE. The decision on which treatment to administer (i.e. RFA vs. TACE) will be made in consultation with the interventional radiologists. The reason for this is that there are technical considerations (size and location of lesion, main portal vein occlusion etc.) which would make one procedure preferable over the other.

Cohort	Population	Immune stimulative procedure	Dose level (Trem)	Planned N
A	Advanced HCC, BCLC Stage C	RFA/TACE	3.5mg/kg	3-6
			10mg/kg	20
B	Intermediate HCC, BCLC B	TACE	10mg/kg	20

- Transarterial chemoembolization is percutaneous procedure performed under general anesthesia or conscious sedation. (See 3.9.1 for details)
- Patients undergoing trans-arterial chemoembolization, RFA or cryoablation are pre-medicated with analgesics, antibiotics and anti-emetics per clinical standards. For details regarding each procedure please see 3.9.
- We will also enroll an additional cohort of N=20 patients (Cohort B) with liver-confined disease for whom TACE is indicated as standard of care. These patients will receive TACE in combination with Tremelimumab using the same schema, although for these patients TACE may be repeated (as per standard of care). They will not receive RFA.
- With protocol amendment F, it was proposed that once cohort A has demonstrated safety and feasibility for the combination of ablative treatment and tremelimumab in HCC, we will add 3 additional cohorts (C-E) to the study. However, with amendment I we have revised the study design to remove Cohort C, so only 2 cohorts, D and E, remain. For these cohorts, the schedule of administration for tremelimumab and the timing of the immune-stimulative procedure is identical to cohorts A and B, as summarized below.

Cohort	Population	Immune stimulative procedure	Dose level (Trem)	Planned N
D	Advanced HCC, BCLC Stage C	Cryoablation	10mg/kg	10

E	Intrahepatic cholangiocarcinoma	RFA	10mg/kg	20
---	------------------------------------	-----	---------	----

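### Cohort A's two 10-patient efficacy tests are defined by the procedure received on Day 36, and the plan does not say which test holds a treated patient who never has the procedure

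*Combined protocol and SAP*

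**What the plan says.** Section 8.1, as changed by Amendment G, makes efficacy the primary objective from then on and splits cohort A at the 10 mg/kg level: "there will be 20 patients enrolled in cohort A at 10mg/kg (10 receiving RFA and 10 receiving TACE"). Each half has its own test. "In each sub-cohort of 10 patients the trial will have 82% power to rule out 15" per cent stable at 6 months, "in favor of 50% being stable at 6 months", on the footing that a "one-sided 0.10 significance level exact binomial test would be performed". The reading offered is that "3 or 4 patients out of 10 attaining stable disease at 6 months with either TACE or RFA would rule out 10-15" per cent.

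The schedule in 3.2 starts tremelimumab on Day 1, every 4 weeks, and then gives "Day 36 [+/- 96 hours]: RFA or TACE". Day 36 is 35 days after the first dose and one week after the second scheduled dose.

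Entry to cohort A (3.3.1) requires disease amenable to one or other procedure and does not name which. On the choice, 3.1 says: "The decision on which treatment to administer (i.e. RFA vs. TACE) will be made in consultation with the interventional radiologists". It gives technical reasons (lesion size and site, portal vein occlusion) and no date for the decision. Inclusion criterion 2.1.1.3 adds: "Each case will be discussed at GI tumor board with interventional radiology".

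Section 6.3.1.2 makes a patient evaluable for response after one cycle and a re-evaluation, or on objective progression before the end of cycle 1. It does not require the procedure. Section 8 does not say where a treated patient without a procedure is counted.

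**The concern.** The 6-month outcome concerns patients treated from Day 1, but membership of a test is worded by something that happens five weeks later. In those weeks a patient can progress, die, withdraw or stop for toxicity (3.9.2 and 3.12.1 list the grounds for stopping treatment). Such a patient has received neither RFA nor TACE. Defining *evaluable* better would not settle the matter, because the patient would still have no sub-cohort.

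If the groups are filled until 10 patients have received each procedure, both denominators are conditioned on getting through the first five weeks. The 15% reference rate carries no such condition: 8.2 presents 10–15% as the share of similar patients stable at 6 months. Recipients would then be compared with a benchmark set too low for them, in two small tests that now carry the primary objective.

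**Working it through.** **Inputs.** From 8.1: n = 10 per sub-cohort, null 15%, alternative 50%, one-sided 0.10, exact binomial. From 3.2: procedure on Day 36. The share of treated patients who never reach the procedure, d, is not in the documents, so it is an assumption, taken over 0 to 30%.

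**Step 1: reproduce the plan.** P(X ≥ 4) = 1 − Σ C(10,k) p^k (1−p)^(10−k), k = 0 to 3.
- At p = 0.50: 1 − (1 + 10 + 45 + 120)/1024 = 848/1024 = 0.828, which matches the stated 82%.
- At p = 0.15: 0.050.
- The looser cut-off of 3 of 10 has error 0.180 at 15%, so 4 of 10 is the rule that meets one-sided 0.10.
- The plan's lower 90% bounds also reproduce: 11.6% for 3/10 and 18.8% for 4/10.

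**Step 2: count recipients only.** Of N treated patients, 0.15N are stable at 6 months under the null and (1 − d)N reach the procedure. If none of those lost would have been stable, the rate among recipients is 0.15/(1 − d). The group size stays at 10 if non-recipients are replaced. Section 8.4 leaves room for that, with a ceiling of 90 against 26 + 20 + 10 + 20 = 76 evaluable patients.

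| Assumed loss d | Null rate among recipients | P(≥4 of 10) |
|---|---|---|
| 0 | 15.0% | 0.050 |
| 5% | 15.8% | 0.059 |
| 10% | 16.7% | 0.070 |
| 20% | 18.8% | 0.100 |
| 30% | 21.4% | 0.147 |

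**Step 3: what the documents say about d.** Section 8.2 reports 9 of 10 patients meeting the three-dose goal. Section 8.1 reports that goal met in the first 20, which under its own rule means at least 14. Both figures pool cohorts A and B, and the third scheduled dose falls on Day 57, so neither measures loss before Day 36. The first suggests a loss near 10%; the second would allow more.

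As an upper illustration, take exponential progression with 15% stable at 6 months. The share progression-free after 35 days (1.15 months) is 0.15^(1.15/6) = 0.695, so about 30% would have progressed. Excluding all of them gives 0.15/0.695 = 21.6% and P(≥4 of 10) = 0.150. This is a ceiling: most such progression would be undetected at Day 36 and need not prevent the procedure.

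**Step 4: does one patient change the result?** Exact one-sided p-values against 15%:
- 4/10: 0.050. Remove one failure, 4/9: 0.034. Add one failure, 4/11: 0.069. All are below 0.10.
- 3/10: 0.180. Remove one failure, 3/9: 0.141. Both are above 0.10.

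Shifting one failure does not by itself change either conclusion.

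**The case against.** The strongest reply is that this is a narrow gap in wording. Section 8.1 speaks of patients enrolled, 6.3.1.2 keeps early progressors evaluable, and the error at a 10% loss (7.0%) is inside the plan's own 0.10. The trial is a small pilot, and 8.3 treats comparison of procedures as informal. The point about size stands: the rise from 5.0% starts from slack left by the discreteness of a 10-patient test. But 6.3.1.2 does not place an early progressor in either sub-cohort, so the denominators remain undefined.

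A reader might go further and infer three things that the documents do not support.

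- *That the RFA/TACE choice follows early disease course.* This is possible, since nothing locks the choice, but it is not shown. The stated reasons are technical, interventional radiology reviews each case as an entry condition, and the first scheduled restaging (every 8 weeks) falls after Day 36. No text dates the decision to Day 36; only the procedure is dated. The study calendar in 3.11 was available only in part, so any imaging it schedules before the procedure could not be checked.
- *That the bias always favours treatment.* That holds only if every early loss would have been non-stable. Footnote a in 3.9 keeps patients who permanently stop tremelimumab on study with disease assessment scans, so some could be stable at 6 months.
- *That moving one patient flips a 4/10 result.* Step 4 shows that it does not.

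**Conclusion.** The point holds in limited form. The two primary efficacy tests in cohort A use groups worded by an event 35 days after treatment starts, and the plan gives no rule for a treated patient who never reaches it. That patients without a procedure belong to neither test is the literal reading of 8.1 but is not stated; the accurate description is that their sub-cohort and denominator are undefined.

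The effect is modest at plausible losses: error 7.0% at 10% loss, 10.0% at 20% and 14.7% at 30%, against 5.0% with none. These figures assume that losses are replaced and that all would have been non-stable, with a loss rate that the documents do not supply. The change is still worth making, because it removes the dependence on that unknown rate at almost no cost.

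**What to change.** Record the intended procedure at the tumour board already required by 2.1.1.3, and assign each patient to A-RFA or A-TACE before dose 1. Add to 8.1, in substance:

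> The primary 6-month analysis of each cohort A sub-cohort includes all treated patients from Day 1, by intended procedure. Patients without the procedure stay in the denominator, are classified by observed 6-month status where assessed, and count as not stable where it is not. Results by procedure received are a sensitivity analysis.

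Using observed status where it exists avoids scoring as failures patients who stopped treatment but are still being scanned.

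For patients already treated, use intended procedure only where it was documented before dose 1. Assignment from notes once outcomes are known would bring in a new bias. Where there is no such record, report cohort A at 10 mg/kg as all treated patients combined, alongside the results by procedure received.

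With 10 patients per assigned group, the plan's figures are kept: 4 of 10 has error 0.050 at 15% and power 0.828 at 50%. The cost is one registration field and possibly a slightly lower observed rate. If the 50% target was meant for procedure recipients and no lost patient is stable, the rate in all treated patients is 0.50 × (1 − d). Power is then 0.734 at 10% loss (45%) and 0.618 at 20% loss (40%), so 8.1 should also say to which population the 50% applies. No treatment changes.
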